An adverse event is any untoward medical occurrence in a subject who has received an intervention (drug, biologic, or other intervention). The occurrence does not necessarily have to have a causal relationship with the treatment. An AE can therefore be any unfavorable or unintended sign (including an abnormal laboratory finding, for example), symptom, or disease temporally associated with the use of a medicinal product, whether or not considered related to the medicinal product. Adverse event monitoring for the emergency department phase would start at the time of randomization and end at two hours after initial medication administration. Any additional adverse events that occur beyond 120 minutes after initial medication administration will be obtained during the 30 day follow up phone call.

All AEs (including serious AEs) will be noted in the study records and on the case report form with a full description including the nature, date and time of onset, determination of non-serious versus serious, intensity (mild, moderate, severe), duration, causality, and outcome of the event. SAEs will be reported within 24 hours.

Definition of a Serious Adverse Event (SAE)

An SAE is any adverse drug experience occurring at any dose that results in any of the following outcomes:

- death
- a life-threatening event (at risk of death at the time of the event)
- requires inpatient hospitalization or prolongation of existing hospitalization
- a persistent or significant disability/incapacity
- results in a congenital anomaly or birth defect

Important medical events that may not result in death, be life-threatening, or require hospitalization may be considered a serious adverse drug event when, based upon appropriate medical judgment, they may jeopardize the subject and may require medical or surgical intervention to prevent one of the outcomes listed in this definition. The one exception to these criteria is hospitalization for repair and/or pain management associated with the injury. Since this can be expected as part of the standard treatment course for orthopedic injuries, admissions for this reason will not be reported as a serious adverse event. However, all admissions will be tracked and those related to adverse events or for reasons other than injury repair or pain management will be reported as an SAE.

Serious adverse event monitoring starts at the time of consent and ends at the time of discharge or admission. All SAEs will be followed until resolution, the event is considered to be medically stable, or for 30 days after the subject completes the study, whichever occurs first.

A distinction should be drawn between serious and severe AEs. A severe AE is a major event of its type. A severe AE does not necessarily need to be considered serious. For example, nausea which persists for several hours may be considered severe nausea, but would not be an SAE. On the other hand, a stroke that results in only a limited degree of disability may be considered a mild stroke, but would be an SAE.

Serious Adverse Events (SAEs) Specific to this Study

There has been documentation of a few significant adverse effects associated with the medications included in this study. These effects are exceedingly rare and are anticipated to be even rarer through an intranasal route of drug administration compared with an intravenous route and with sub-dissociative dosing of ketamine as compared with dissociative dosing.

Ketamine: cardiac arrhythmia, hypertensive emergency, prolonged emergence reaction, anaphylaxis, laryngospasm, apnea

Fentanyl: cardiac arrhythmia, cardiopulmonary arrest, chest wall rigidity, hypertensive emergency, hypotension, pulmonary embolism, anaphylaxis, apnea, bronchospasm, laryngospasm

In the exceedingly rare instance that one of these serious adverse effects was to occur, the patient would be treated for that particular emergency in a manner that is standard of care at CCHMC were the emergency to occur in any other setting.

Relationship of SAE to study drug or other intervention

The relationship of each SAE to the study intervention should be characterized using one of the following terms in accordance with CCHMC IRB Guidelines: definitely, probably, possibly, or unrelated.

Monitoring Plan

The medical monitor is the person responsible for the safety monitoring in this protocol and he will monitor all clinically significant adverse events (AEs) and provide consultation for any AEs that the investigators question the classification, severity or relatedness originally documented at the time of the ED visit. The medical monitor will be [name]. He is a member of the Division of Emergency Medicine, who will not be involved with enrollment.

A risk-based monitoring plan will be developed for the conduct of study monitoring. On-site monitoring will occur throughout the duration of the study. A study initiation visit will be conducted by the study monitoring staff to ensure that the study staff have been completely trained in protocol procedures and Good Clinical Practices (GCP) and that facilities and personnel are adequate. Scheduled monitoring will occur at least once per year during the conduct of the trial, with the option of making a second visit if needed to address over-enrollment, under-enrollment, or protocol deviation issues. The Monitoring Plan will detail the frequency and level of intensity of on-site monitoring visits. In general, the study will be monitored for all subjects at a level of 100% of study data gathered for inclusion and exclusion criteria, informed consent procedures, and adverse events. At a minimum, at least 20% of the study subject's data will be monitored against the study's database.

During scheduled interim monitoring visits, the monitors will verify that the protocol is being followed and that data are being collected according to protocol requirements. The monitors will review the Study Regulatory File to determine that all required documentation is being collected and that the IRB approval for the study is current. They will then verify that each subject has signed the correct version of the informed consent document, and that this document is filed in the subject's file. Adverse event documentation is checked for completeness and accuracy. Drug and supplies accountability will also be monitored. At the study closeout, the monitors confirm that all data have been reviewed, all source documents have been verified, and all required documents are present in the Study Regulatory File. The table below describes the variables to be reviewed during monitoring visits.

Variable	% of Records Reviewed
Informed consents	100%
Eligibility criteria for all screened subjects	100%
Adverse events	100%
Drug accountability	20% of active subjects
Protocol adherence	20% of active subjects
Verification of eCRFs with source documents	20% of active subjects

Central study files-inclusion of all applicable documents	100%
Protocol deviations/violations	100%

AEs will be reported to the IRB as detailed below. Adverse events will be recorded on the study data form by the study team. Any serious adverse events (SAEs) will be reported to the investigator or designee immediately. Study forms and charts will be reviewed by the study coordinator and principal investigator for AEs after the ED visit. All identified AEs will be recorded. The investigator will determine the grade and attribution. If unblinding is required, the investigator will notify the IRB. The protocol and consent will be reviewed by the investigator to determine if any changes are required. SAE's that are related to the study and unexpected will be reported to the IRB and FDA. Any serious adverse events and/or adverse events that occur during the study will be followed to resolution.

For the purpose of this study, toxicity is defined using the Common Terminology Criteria for Adverse Events (CTCAE) v4.0 as defined by the National Cancer Institute (<http://ctep.cancer.gov/reporting/ctc.html>).

Grade level 4 or greater toxicity which are unexpected and related to the study will be reported to the IRB within 48 hours. Examples pertinent to this protocol include: life threatening respiratory compromise resulting in intubation, anaphylaxis, hypotension, hypertensive crisis, life-threatening cardiac arrhythmias requiring urgent intervention, nausea and emesis with life-threatening consequences, and change in mental status including states harmful to the subject.

Subjects will be withdrawn from study drug exposure if any of the following events occur during the patient's stay in the ED:

- The subject has a SAE possibly or definitely related to the study drug
- The subject experiences a level 4 toxicity as defined by CTCAE
- The subject experiences one or more level 3 toxicities as defined by CTCAE
- The subject has an adverse event experience that would, in the investigator's judgment, make continued participation in the study not in the subject's best medical interest.

The trial will stop enrollment for the following events:

- A SAE rate related to the study intervention of greater than or equal to 2 in 10 subjects is detected
- Subjects experiencing grade 3 toxicities occur more frequently than 3 in 10 subjects.

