Graudins, 2015 Ketamine for analgesia (sub-dissociative low dose)	73	3-13 years	Emergency Department, Australia	Double blind, randomized controlled trial: Fentanyl vs Ketamine	Fentanyl 1.5 mcg/kg Ketamine 1 mg/kg	IN	Median reduction in VAS score at 30 minutes for ketamine was 45 mm and for fentanyl was 40 mm (no significant difference between groups), which was maintained to 60 minutes in both groups.	Fentanyl: Bad Taste 42% Drowsiness 21% Dizziness 17% Itchy nose 12% Nausea 4% Dysphoria 4% Hallucinations 0% Ketamine: Bad Taste 25% Drowsiness 16% Dizziness 30% Itchy nose 4% Nausea 6% Dysphoria 4% Hallucinations 6%
Yeaman, 2013 Ketamine for analgesia (sub-dissociative low dose)	28	3-13 years	Emergency Department, Australia	Observational study: Ketamine	Ketamine 0.8-1.48 mg/kg	IN	IN ketamine provided adequate analgesia by 30 minutes. Median VAS decreased from 74.5 mm to 30 mm.	Dizziness 36% Bad taste 29% Dysphoria 14% Nausea 11% Sore throat 7% Diplopia 7% Amnesia 4% Headache 4% Vomiting 4%
Johansson, 2013 Ketamine for analgesia (sub-dissociative low dose)	9	7-36 years	Prehospital trauma, Sweden	Case series: (S)-Ketamine	Ketamine 0.45 mg/kg-1.25 mg/kg	IN	IN S-ketamine provided adequate analgesia. Median pain score decreased from 10 to 3 (on a 10 point scale).	Vertigo Unpleasant taste
Tsze, 2012 Ketamine for sedation	12	1-7 years	Emergency Department, USA	Randomized, prospective double blind trial: Ketamine (3 doses)	Ketamine #1 3 mg/kg Ketamine #2 6 mg/kg Ketamine #3	IN	Significantly higher proportion of successful sedations with 9 mg/kg dose than	Vomiting 8%

(dissociative dosing)					9 mg/kg		the other two doses.	
Gyanesh, 2013 Ketamine for sedation (dissociative dosing)	150	1-10 years	Radiology (MRI), India	Randomized double blind trial: Dexmedetomidine (DXM) vs Ketamine vs Normal saline	DXM 1 mcg/kg Ketamine 5 mg/kg Normal saline	IN	DXM and ketamine were equally effective as pre-medication. In 90.4% of DXM patients and 82.7% of ketamine patients, satisfaction with conditions for IV insertion. Total dose of propofol used was less in DXM and ketamine groups.	DXM: Bradycardia 4% Nausea/Emesis 4% Ketamine: Nausea/Emesis 10% Saline: Nausea/Emesis 6%

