The sample size calculation is based on a non-inferiority test of the difference between two means. Group sample sizes of 39 and 39 achieve 80% power to detect non-inferiority using a one-sided, two-sample t-test. The margin of non-inferiority is 10. Literature has shown that the minimum clinically significant difference in VAS pain score in children is 10-12 [65, 66] which is why 10 was chosen as our non-inferiority margin. The true difference between the means is assumed to be 5 based on the PICHFORK trial, which found a median rating reduction of 40 mm (IQR 20 to 45) at 30 minutes for fentanyl and a median rating reduction of 45 mm (IQR 20-60) at 30 minutes for ketamine, and therefore, a difference in medians of 5 (-10 to 20, 95% CI) [60]. Using the IQR information from the PICHFORK trial and assuming normality for the pain scores, we estimate the standard deviations to be 29.63 and 22.22 for the rating reduction at 30 minutes for the fentanyl and ketamine groups, respectively. Therefore, with an α of 0.05 and a β of 0.2 (80% power), the sample size required to detect this difference was estimated to be 39 subjects in each group, for a total of 78 subjects. In order to achieve this number of evaluable subjects, we plan to enroll 90 subjects, anticipating that not all subjects enrolled will be fully evaluable. Over the last year, there were 634 patients who presented to the CCHMC ED and were triaged as orthopedic evaluations. Of these, 360 were in the age group specified in the inclusion criteria. Given this data, we expect to be able to successfully complete this study as planned.

VII. STUDY PROCEDURES

Table 4. Study Procedures

Visits	Visit 1						Visit 2
	Screening Phase	Enrollment	15 (±5) min	30 (±5) min	60 (±5) min	120 (+30) min	+30 (±5) days *
Informed Consent, Assent for subjects ages 12-17		X					
Review Inclusion/Exclusion Criteria	X						
Demographics/Medical History	X						
Physical Examination	X						
Vital signs (HR, RR, BP, O2 sat)		X	X	X	X	X	
Serum or urine pregnancy test for postmenarchal females	X						
Weight	X						
VAS pain score		X	X	X	X		
UMSS sedation score		X	X	X	X		
Nasal mucosal exam	X					X	
Smell test	X					X	
Capnometry value		X	X	X	X		
Randomization		X					
Dispense study drug		X					
Adverse event/Serious adverse event assessment		X	X	X	X	X	X

*Visit 2 window +/- 5 days.

(See Appendix C for study flow diagram, Appendix D for current orthopedic evaluation flow diagram, and Appendix E for duration of study procedures)

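### The planning SDs do not follow from the IQRs printed beside them, and the 80% power holds only if ketamine is truly 5 mm better, which the text leaves unsaid

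*Combined protocol and SAP*

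**What the plan says.** The calculation is in section VI under Sample Size and Power Analysis. It states that "Group sample sizes of 39 and 39 achieve 80% power to detect non-inferiority using a one-sided, two-sample t-test" and that "The margin of non-inferiority is 10" (mm on the VAS). One-sided alpha is 0.05. On the effect it says "The true difference between the means is assumed to be 5 based on the PICHFORK trial".

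Two source figures are printed there. The comparator's is "a median rating reduction of 40 mm (IQR 20 to 45) at 30 minutes for fentanyl". The intervention's, given next in the same sentence, is "a median rating reduction of 45 mm (IQR 20-60) at 30 minutes for ketamine". The gap between the two medians is put at 5, and its 95% CI runs from -10 to 20. From those IQRs, assuming normality, the plan says "we estimate the standard deviations to be 29.63 and 22.22 for the rating reduction at 30 minutes for the fentanyl and ketamine groups, respectively". The result is 39 evaluable subjects per group, 78 in total, with 90 to be enrolled.

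Table 2 in the Background repeats the source medians: "Median reduction in VAS score at 30 minutes for ketamine was 45 mm and for fentanyl was 40 mm (no significant difference between groups". Hypothesis #1 in section II expects the two drugs not to differ significantly in mean pain reduction.

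**The concern.** There are two separate points.

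**The SDs.** The section gives the method, the inputs and the outputs together, and they do not agree. Neither arm's SD follows from that arm's IQR, and one of the two follows from neither. These SDs are the stated basis for N, so a reader cannot tell which figure to trust.

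**The sign of the 5 mm.** In a non-inferiority test, the sign of the assumed true difference decides how far the truth lies from the margin: 15 mm if ketamine is 5 mm better, 10 mm if the drugs are equal, 5 mm if ketamine is 5 mm worse. The plan gives 5 without a sign and reports no power at equality. A reader who takes 80% to be the chance of success when the drugs are equally effective would be misled, and a failed non-inferiority result would be hard to interpret.

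**Working it through.** **Inputs** (all from Sample Size and Power Analysis; 1:1 allocation from Randomization and Blinding): margin 10 mm; one-sided alpha 0.05; SDs 29.63 (fentanyl) and 22.22 (ketamine); IQRs 20 to 45 (fentanyl) and 20 to 60 (ketamine); assumed difference 5 mm; 39 per arm; 90 enrolled.

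**Step 1: SD from IQR.** Under normality the IQR is about 1.35 SD, so SD = width / 1.35. The divisor 1.35 reproduces the plan's 29.63 exactly, whereas 1.349 would give 29.65.

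| Arm | Printed IQR | Width | Width / 1.35 | Plan's SD | Width the plan's SD implies |
|---|---|---|---|---|---|
| Fentanyl | 20 to 45 | 25 | 18.52 | 29.63 | 29.63 × 1.35 = 40 |
| Ketamine | 20 to 60 | 40 | 29.63 | 22.22 | 22.22 × 1.35 = 30 |

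Swapping the labels would put 29.63 in the right place but leave 22.22 where 18.52 should be.

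**Step 2: reproduce the plan's N.** SE = √((s₁² + s₂²)/n). With the plan's SDs and n = 39, SE = √((877.94 + 493.73)/39) = 5.93. Power comes from the noncentral t with df = 2n − 2 = 76 and noncentrality = (distance to margin)/SE.

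- Ketamine 5 mm better: distance 10 + 5 = 15, noncentrality 15/5.93 = 2.53, power 80.6%. At 38 per arm it is 79.6%, so 39 is the smallest n that reaches 80%. The plan's figure reproduces.
- Equal: distance 10, power 51.0%; 80% needs 86 per arm.
- Ketamine 5 mm worse: distance 5, power 20.9%; 80% needs 340 per arm.

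Only the first direction gives 39. Welch degrees of freedom give the same sample sizes. One-sided alpha 0.025 would need 49 per arm even with ketamine 5 mm better, so 0.05 is the level that was used.

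**Step 3: repeat with the IQR-derived SDs (18.52 and 29.63).** At n = 39, SE = √((342.94 + 877.91)/39) = 5.59. For 80% power, 35 per arm suffices if ketamine is 5 mm better, and 77 per arm are needed if the drugs are equal.

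**Step 4: power side by side**, at the planned 39 per arm and at 45 per arm (all 90 evaluable).

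| True difference (ketamine minus fentanyl, mean reduction) | Plan SDs, 39 | Plan SDs, 45 | IQR-derived SDs, 39 | IQR-derived SDs, 45 |
|---|---|---|---|---|
| +5 mm | 80.6% | 85.3% | 84.4% | 88.7% |
| 0 | 51.0% | 56.1% | 55.0% | 60.3% |
| −5 mm | 20.9% | 22.8% | 22.4% | 24.4% |

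Which SD belongs to which arm does not affect these figures, because with equal arms only the sum s₁² + s₂² enters the SE.

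**The case against.** The strongest reply is that the SD fault is harmless. If the SDs are right and an IQR is misprinted, N and power do not change. If the IQRs are right, 39 per arm is more than the 35 needed. One of the two SDs also does come from a printed IQR, attached to the wrong arm. All of that stands, and it is why this is a correction to the text and not a case for more patients. It does not make the paragraph consistent: 22.22 still has no printed source.

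A second reply is that the sign is not hidden. The medians, 45 for ketamine and 40 for fentanyl, stand next to the assumed 5, and only one direction reproduces 39. That also stands. Planning on an expected advantage is legitimate, and omitting other scenarios is a reporting gap, not an arithmetic error. But power at equality is worth printing because the plan's own hypothesis expects no significant difference, the source interval (−10 to 20) includes 0, and the source trial found no significant difference.

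A third reply concerns the replacement figures. The printed quartiles are asymmetric: for fentanyl the median of 40 lies 20 above the lower quartile and 5 below the upper. An SD obtained by width / 1.35 is therefore rough, and 35 per arm and 84.4% hold only under the plan's own normality assumption. This caveat should accompany those figures, but it does not explain the mismatch.

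**Conclusion.** The concern holds. Under the plan's own method, the SDs should be 18.52 (fentanyl) and 29.63 (ketamine), against the stated 29.63 and 22.22. Either at least one SD or at least one IQR is wrong, or 22.22 has a source that is not given; the documents cannot settle which. The effect on the design is small and in the safe direction: power at 39 per arm with ketamine 5 mm better is 80.6% with the stated SDs and 84.4% with the IQR-derived ones.

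The larger practical point is that the 80% is conditional on a 5 mm ketamine advantage. If the drugs are equal, the trial has a 51.0% to 55.0% chance of showing non-inferiority at 39 per arm, and 56.1% to 60.3% if all 90 are evaluable. These figures assume normal data, a 10 mm margin, one-sided alpha 0.05 and the t-test named in the plan.

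**What to change.** 1. Check the SDs and IQRs against the cited trial report. Correct whichever is misprinted, or give the source of 22.22, and make the arm labels agree.
   - If the printed IQRs stand, the SDs become 18.52 (fentanyl) and 29.63 (ketamine), and the text should say 35 per arm for 80% power, or 84.4% at 39, noting that the normal conversion is approximate for these quartiles.
   - If 29.63 and 22.22 stand, N and power do not change; only the IQRs or the labels need correcting.
2. Add a sentence with figures that match the reconciled SDs. With the plan's SDs it could read: *The 80% power assumes that ketamine's mean reduction is 5 mm greater than fentanyl's; if the true difference is 0, power is about 51% with 39 per group and about 56% with 45 per group.*

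Keep enrolment at 90. Disclosure does not raise power at equality, which would take 86 per arm with the plan's SDs, but it makes the assumption visible to anyone reading the result. The cost is a source check and two or three sentences, and a less favourable power figure appears in print. The analysis does not change.
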